9.1 Background

Epidemiological studies have suggested a strong correlation between smoking and alcohol use (106). Specifically, it has been estimated that 20–25% of smokers are also heavy alcohol users (107), and this co-occurrence has been associated with poorer outcomes in terms of physical health and smoking cessation quit rates (107, 108). In the context of a quit attempt, alcohol use has been associated with increased risk for a smoking lapse, such that heavy drinking smokers are 4 times more likely to experience a smoking lapse in the context of a drinking episode and 8 times more likely to lapse in the context of a heavy drinking episode (108).

Several theories have been proposed to explain the strong co-occurrence of alcohol and cigarette use. For example, participants with a past history of alcohol dependence have reported greater reinforcement from nicotine administration as compared to those who were never alcohol dependent (109). Given that baclofen is a GABAergic agent that has been shown to reduce cue-induced craving and brain activity in reward-related regions, baclofen may have a similar effect on alcohol cue-induced craving. To date, however, there are no studies examining the effects of baclofen on brain and behavioral responses to both smoking and alcohol cue reminders in cigarette smokers seeking smoking cessation treatment who drink heavily. As such, this sub-study will yield novel findings on baclofen's effects on brain and behavioral responses associated with co-occurring alcohol and tobacco use.

9.2 Risk/Benefits

Potential Risks

This sub-study is part of a larger, ongoing study described above. As such, the potential risks are the same as the larger study.

Potential Benefits

In addition to the benefits described in the larger, ongoing study, this sub-study benefits society by providing information and a potential improvement in the effectiveness of treatment for problem drinking in cigarette smokers, which may reduce the personal and societal costs associated with these problems.

Risk Benefit Ratio

The potential benefits of this study far outweigh the potential risks. Co-occurring alcohol and tobacco use is a serious concern with only mildly effective pharmacotherapy. Even in the best programs, relapse rates are high. Individuals accepted into this study will receive close medical and psychiatric monitoring. Subjects will be screened prior to admission into the study and those at risk for adverse reactions will be excluded.

10. Sub-Study Objectives

Objective 1: Examine the effects of baclofen on brain responses to alcohol cues (compared to non-alcohol cues) and drinking behavior compared to placebo following 4 weeks of baclofen or placebo in individuals actively seeking smoking cessation treatment and drink heavily.

Hypothesis 1: Baclofen will modulate resting brain activity—specifically, activity in the lateral orbitofrontal cortex. Baclofen will also modulate alcohol cue reactivity: activity in reward-related regions will be blunted in subjects receiving baclofen, while those receiving placebo will display the original signature of craving. Baclofen will correct vulnerabilities by modulating neural activity in the amygdala and ventral striatum, regions known to respond to reward and in the insula, which is considered an autonomic signaling relay station and plays a role in drug craving.

11. Sub-study Design

11.1 General Design

This optional sub-study involves adding one additional MRI scanning session to the larger, ongoing main study (described above). Twenty (20) individuals who are seeking smoking cessation treatment and drink heavily (drinking five or more alcoholic drinks on the same occasion on five or more days in the past 30 days). The additional scan will occur after 4 weeks of baclofen or placebo and will follow most of the same procedures as the previous two scan sessions; however, instead of viewing smoking cues, subjects will view alcohol cues.

11.2 Primary Study Endpoints

The primary endpoints to be measured include:

- Self-report ratings of cues, subjective ratings of craving during/following cue exposure, and neuroimaging data on cerebral blood flow when the brain is at rest and when exposed to alcohol cues.

12. Sub-study Subject Selection

12.1 Inclusion Criteria

- 1) Subjects have consented to main study protocol and are eligible to randomize to study drug.
- 2) Provide voluntary informed consent.
- 3) Consume five or more alcoholic drinks on the same occasion on five or more days in the past 30 days.

12.2 Exclusion Criteria

- 1) See exclusion criteria for main study

12.3 Subject Recruitment and Screening

Subjects will be recruited from those who respond to our advertisements for the main study. Following the consent of the main study, potential subjects will provide information on recent substance use through administration of the Addiction Severity Index (ASI). If the potential subject reports consuming five or more alcoholic drinks on the same occasion on five or more days in the past 30 days, s/he will be flagged as a potential participant for the sub-study. If the individual shows continued interest in participating in the study, an appointment will be made for further screening at the Center for Studies on Addiction (CSA). The CSA initial screening process will be described, and the individual will also be informed that s/he must be available for at least two separate appointments during the screening week (unless the two appointments are combined) (see the Physical Examination Visit and Psychological Evaluation Visit sections pg 10-11 for more information). Potential subjects will be informed that all information obtained will be used to determine his/her final eligibility for main and sub-study participation. If the individual does not qualify for the study, s/he will be provided with appropriate community smoking cessation referrals.

12.4 Informed Consent Visit

Subjects will undergo the informed consent process for the sub-study once their 1st MRI session imaging data is able to be reviewed. Once their eligibility is confirmed, an in depth explanation of the study procedures, its risks, potential benefits, and alternatives to treatment will be discussed with the subject, given their interest in participation. Following resolution of any questions, subjects who appear to understand the nature of the study and consent will be asked to sign the study consent form. A copy of the sub-study informed consent form will be given to each subject. S/he is also reminded that participation is voluntary, and at any time, s/he may withdraw from the main study or sub-study. **Measures and procedures described for the MRI sessions of the main study will be mostly the same for the sub-study's 3rd MRI session visit. The major differences will be the use of alcohol imaging cues, a different craving scale measure pre/post scan (Within-Session Rating Scale-Alcohol (WSRS-Alcohol) and no cotinine testing.**

13 3rd MRI session visit (2 hours)

The 3rd MRI session takes place after a subject has been on the medication for 4 weeks. At this session, the subject will be asked to take their medication in the presence of Study Staff [Baclofen has a short life with maximum effects at 2 hours and waning thereafter. Thus, ingesting the medication in front of study staff will ensure that the medication was ingested and that its effects will be observable during the MRI as well as standardize time since dose]. Stimuli for the 3rd scan will be audio-visual video clips consisting of either alcohol-related or non-alcohol-related cues instead of smoking-related and non-smoking-related cues presented during scans 1 and 2. In addition, subjects will be asked about their craving pre- and post-alcohol cue exposure using the WSRS-Alcohol. Otherwise, this visit will be exactly the same as the previous MRI sessions described above.

At this appointment, the subject will make a quit smoking attempt. To assist the subject in meeting this goal, study staff will meet with the subject to go through the "You can quit smoking" pamphlet during this appointment which is an interactive tool designed to help people recognize relapse triggers, provide alternative strategies when craving occurs, and how to acquire support from friends and family. Explicit instructions for how to conduct this session are included with the uploaded IRB documents (Titled: Smoking Booklet Script). Monitoring of smoking behavior is accomplished with completion and collection of subject Daily Diaries, weekly phone calls with study staff, weekly meetings with study staff, and CO measurements.

14 Sub-study Subject Stipends or Payments

In addition to the payments received as part of the main study, sub-study subjects will receive \$6 for travel expenses and will be paid \$100 for completing the 3rd scan session visit.

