Non-abstinent subjects will be randomized by sex and DAT genotype. We will use our perfusion fMRI/cue paradigm to acquire resting baseline (RB) and SC data to confirm and extend our finding of a DAT-mediated SC-vulnerable endophenotype; 9-repeat carriers will exhibit enhanced brain activity in the interconnected VS/mOFC (regions involved in conditioned drug reward) compared to 10/10-repeats. Behavioral responses, including craving and cigarette consumption, will be significantly greater in 9-repeat carriers compared to 10/10-repeats following SC exposure.

Within the 2 x 2 design (9-repeat carriers vs 10/10-repeats) X (baclofen vs placebo), treatment-seeking subjects will participate in an 8-week medication regimen. Baclofen or placebo will be prescribed to non-abstinent subjects at the same doses that have been demonstrated to be clinically effective in our Smoking Reduction Trial. The importance of subjects being non-abstinent is twofold. First, our goal is to determine if and how baclofen affects SC reactivity independent of WD to disentangle these two major motivators underlying relapse. Second, differences in smoking behavior modulate brain activity, so it is important that baclofen- and placebo-treated groups have similar smoking characteristics.

3. Study Duration

This study requires a one-week screening phase and 8 weeks of monitoring and medication. All subjects will complete 2 MRI sessions (one before starting medication, one following 3 weeks of medication) and 5 weeks of additional treatment. Each subject will be enrolled in the study for approximately 10 weeks.

The entire study will commence 12/01/2012 and will run until 08/31/2017, approximately. 20 to 25 subjects will be randomized each year.

DRUGS OR DEVICES

Baclofen and matching placebo

STUDY PROCEDURES

General Procedures

*Interested potential subjects will be screened with a structured interview. Individuals who may qualify are scheduled for the consenting visit. If the consent is successful, individuals will be scheduled to come in for physical and psychological examinations and to provide a genetics sample.

*After the results of the examinations are reviewed, the subject will be contacted to inform them whether or not they qualify. If the examinations reveal any health problems that require medical attention, the subject will be referred to their family physician.

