*Subjects will then participate in the 1st fMRI session and will complete a Cognitive Bias session described in detail below. At this appointment, subjects will be asked to set a Quit Date to occur one week after the second scanning session.

*Subjects will be randomized as described in detail below and participate in several study procedures over the course of the study.

*After 3 weeks, subjects will participate in the 2nd fMRI session (on treatment condition).

*Subjects will be called and reminded of their Quit Date prior to their next weekly appointment. At this appointment they will receive a "You can quit smoking booklet" and participate in a counseling session aimed at helping them recognize their relapse triggers, find alternative behaviors to engage in and get support from friends and family. They will make an attempt to quit smoking at this time.

*Subjects will continue treatment for a total treatment time of 8 weeks (i.e., 1st fMRI session followed by 3 weeks of medication treatment; 2nd fMRI session and 5 additional weeks of medication treatment).

Specific Procedures (Overview Table provided below description)

1. Initial Telephone Screening Procedures (approximately 30 min) Subjects will be recruited from the Center for the Studies of Addiction (CSA; UPenn), at [name], through local advertisement, social media (Facebook), and "word of mouth". Subjects who express interest by responding to advertising are contacted by phone and participate in a telephone screening interview. The nature of the study, including the number of visits to the center, an fMRI description, subject protections and confidentiality, are described. If the caller is still interested, questions on general health are asked. If the applicant is determined to be eligible based on this screening, s/he is asked

whether they accept or decline to participate. If the caller is still interested, they will be scheduled for an initial consenting appointment.

2. Informed Consent Procedures Visit (approximately 1 to 1.5 hr)

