As with any study in which subjects are asked to take a medication, compliance is an issue. Once a week, the number of pills returned in the blister pack will be subtracted from the number of units dispensed to obtain a measure of the amount of medication consumed by the subject throughout the week. To improve tolerance and thereby compliance, baclofen will be introduced slowly to minimize the possibility of undesirable side effects, such as sedation. The study physician or the nurses under the physician's supervision will monitor administration of study medication. See Dispensation Schedule (below). The key describes how the medication will be administered. P = placebo, O = 10 mg baclofen, X = 20 mg baclofen. There are two pills in every blister. These are packaged by IDS to accommodate the titration and taper. Once the full dose is reached (Day 4) and if a subject experiences discomfort or adverse events that may be related to the medication the dose will be decreased until symptoms remit. This will be accomplished by consultation with the Medication monitoring team (Study Physician and Nurses), who will determine if the adverse events might be medication-related. The subject will then be instructed to only take one of the two pills within each blister and disregard the other pill. This lower dose may be maintained throughout the study if the subject so desires. In our ten years experience with this medication and our ongoing protocol (CURE Protocol # 813953) we have had a few subjects request a reduction in dose so we are prepared for this possibility.

Baclofen Dosing Schedule

Study Day	8 AM	12 Noon	4 PM	8 PM
Day 1	Placebo	10 mg Baclofen	Placebo	10 mg Baclofen

Day 2	Placebo	10 mg Baclofen	10 mg Baclofen	10 mg Baclofen
Day 3	Placebo	20 mg Baclofen	20 mg Baclofen	20 mg Baclofen
Day 4-7	20 mg Baclofen	20 mg Baclofen	20 mg Baclofen	20 mg Baclofen
Week 2 - 7	20 mg Baclofen	20 mg Baclofen	20 mg Baclofen	20 mg Baclofen
Week 8 Day 1-2	Placebo	20 mg Baclofen	20 mg Baclofen	20 mg Baclofen
Week 8 Day 3-4	Placebo	20 mg Baclofen	Placebo	20 mg Baclofen
Week 8 Day 5-6	Placebo	10 mg Baclofen	Placebo	10 mg Baclofen
Week 8 Day 7	Placebo	Placebo	Placebo	Placebo

2nd MRI session Visit (approximately 2 hours)

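### Sub-study consent is tied to review of the Scan 1 images and nothing places it before randomisation or first dose, so entry to the Week 4 baclofen v placebo comparison can be decided after assignment

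*Combined protocol and SAP*

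**What the plan says.** Section 12.4 gives the earliest time for sub-study consent: "Subjects will undergo the informed consent process for the sub-study once their 1st MRI session imaging data is able to be reviewed". No latest time is given.

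The first inclusion criterion in section 12.1 is phrased as though assignment lies ahead: "Subjects have consented to main study protocol and are eligible to randomize to study drug". The drinking criterion is screened earlier still. Under section 12.3, a subject who reports enough heavy-drinking days on the ASI, after main-study consent, "s/he will be flagged as a potential participant for the sub-study".

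In the main protocol, General Procedures lists the first fMRI session and the cognitive bias session, and the next item reads: "Subjects will be randomized as described in detail below and participate in several study procedures over the course of the study". The same list describes the treatment course as "1st fMRI session followed by 3 weeks of medication treatment". Study Duration describes the two main scans as "one before starting medication, one following 3 weeks of medication". The paragraph on randomisation and dispensing sits within the description of the 1st MRI visit.

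The sub-study outcome scan comes later. Section 13 says: "The 3rd MRI session takes place after a subject has been on the medication for 4 weeks". Section 10 makes the objective a comparison of baclofen with placebo, and section 11.1 sets the size at 20.

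**The concern.** A comparison of randomised arms is protected when membership of the analysis set is settled before assignment, or cannot be influenced by it. Here the decision to join can come after a subject has begun taking baclofen or placebo. Blinding hides the label but not sedation or a perceived change in craving. The Background section gives drowsiness of 10-63% on baclofen, and the dosing text says of earlier experience that "we have had a few subjects request a reduction in dose". If such effects alter willingness to return for another scan, and do so differently by arm, the two groups scanned at Week 4 may differ for reasons other than the drug's effect on alcohol-cue response.

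The sub-study is poorly placed to detect this. It has one alcohol-cue scan, on treatment, and no pre-treatment alcohol-cue scan to compare or adjust with. The plan also does not ask for take-up among flagged subjects to be reported by arm.

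**Working it through.** **1. Order of events.** No date or interval is given for randomisation, first dose or sub-study consent, so the order has to be read from the text.

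| Step | Where | What is fixed |
|---|---|---|
| Heavy-drinking flag (ASI) | 12.3; Informed Consent Procedures Visit | Before Scan 1 and before drug |
| Scan 1 | Study Duration | Before medication |
| Randomisation | General Procedures; randomisation paragraph | Listed directly after Scan 1; described under that visit |
| Medication | General Procedures | Three weeks follow Scan 1; no gap described |
| Sub-study consent | 12.4 | Not before Scan 1 images can be reviewed; no upper limit |
| Alcohol-cue scan | Section 13 | After 4 weeks on medication |

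Consent before assignment requires image review, consent and randomisation to occur in that order, either within the Scan 1 visit or in a gap the plan does not describe. Nothing forbids that order and nothing requires it. The Table of Measures does not settle the matter. It has no row for randomisation or sub-study consent, and its medication-monitoring row is marked at Scan Visit 1 but also at the pre-drug evaluation visit.

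**2. Precision.** The plan gives no power calculation for the 20 subjects, so there is no figure to reproduce. At the protocol's 2:1 ratio, 20 x 2/3 = 13.3 and 20 x 1/3 = 6.7, or about 13 v 7. In SD units the standard error of the arm difference is sqrt(1/13 + 1/7) = 0.469.

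**3. Scale of a possible shift.** The documents supply neither take-up nor its relation to outcome, so both are assumed. Suppose a proportion q of the baclofen subjects invited join, those with the highest willingness, and willingness correlates r with outcome. Suppose also that joining in the placebo arm is unrelated to outcome. The baclofen mean then shifts by r x phi(z)/q, where phi is the standard normal density and z cuts off the upper fraction q.

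| Take-up q | phi(z)/q | Shift, r = 0.3 | Shift, r = 0.5 | Two-sided type I error at nominal 0.05 |
|---|---|---|---|---|
| 80% | 0.350 | 0.105 SD | 0.175 SD | 0.055-0.064 |
| 67% | 0.541 | 0.162 SD | 0.270 SD | 0.062-0.085 |
| 50% | 0.798 | 0.239 SD | 0.399 SD | 0.077-0.127 |

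The last column is for a two-sample t test at 13:7. With r = 0, or with the same take-up and correlation in both arms, the net shift is zero and the error stays at 0.05. An intermediate case has 50% take-up on baclofen, 80% on placebo and r = 0.5 in both; the net shift is 0.399 - 0.175 = 0.224 SD.

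**The case against.** A reader might infer that sub-study subjects are ordinarily already randomised and on drug when they consent. The documents do not establish this. Criterion 1 in section 12.1 reads naturally as a pre-assignment condition. The Scan 1 visit lasts about three hours, including about an hour of computer tasks, so a same-day image check followed by consent and then randomisation is possible. The defensible statement is that consent after assignment is likely and is not prevented.

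A reader might also infer that the comparison is no longer between randomised groups. That goes too far. Every participant is randomised, drinking is screened before drug, and treatment is blinded. Bias needs joining to depend on arm and to relate to outcome, and no section shows that it does. The Background section reports no side-effect difference between arms in the investigators' earlier smoking-reduction trial, nor in a multi-site cocaine trial with the same schedule. This weakens the side-effect route but leaves perceived benefit open. The third scan is paid and falls on the quit-week visit, which limits its added burden in either arm.

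Baseline checks are not wholly absent. Resting CBF is a sub-study endpoint (section 11.2) and is measured at Scan 1, as are the AUQ and a 30-day TLFB. These can reveal some imbalance but do not replace a baseline alcohol-cue response.

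On size, Appendix 1 cites 20-25% of smokers as heavy drinkers. Among 100 randomised that is 20-25 candidates, so enrolling 20 would need 80-100% take-up and leave little room for selection. The sub-study joins a trial already under way, however, so its pool is smaller, and take-up is unconstrained if 20 is not reached. The main study's effect size of 0.78 is no yardstick for the shift: it is a DAT-genotype effect on smoking-cue response, not a baclofen effect.

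Finally, earlier consent does not stop selective withdrawal before Week 4. That stands, and the fix has to allow for it.

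**Conclusion.** The point holds as a gap in the plan, not as a demonstrated bias. Section 12.4 permits, and the order of main-study events makes likely, consent after assignment; section 12.1 implies the reverse, and the two must be reconciled. The consequence is conditional: the Week 4 comparison loses the protection of randomisation only if joining depends on arm and relates to outcome. Under the assumed one-arm scenarios the shift is about 0.1-0.4 SD, in every case below the standard error of about 0.47 SD, and it may be zero. Those figures show scale and do not estimate what will happen. The main-study aims are unaffected. A change is still worth making, because this is the sub-study's only treatment comparison, the baseline checks are partial, and the remedy costs almost nothing.

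**What to change.** Amend section 12.4 so that sub-study consent is signed before treatment is assigned, either at the main consent visit once the ASI flag is known (conditional on final eligibility) or at Scan Visit 1 before randomisation. This brings 12.4 into line with criterion 1 in section 12.1. State the order of sub-study consent, randomisation and first dose explicitly in both the appendix and General Procedures.

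Keep the Scan 1 image review as a pre-treatment quality check that may exclude a consented subject. Define the sub-study set as all who consented before assignment and were randomised. Report by arm the number not scanned at Week 4, with reasons, because later withdrawal can still be selective.

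If earlier consent is not adopted, report take-up among flagged subjects by arm, compare the arms on Scan 1 resting CBF, AUQ and TLFB, and label the comparison exploratory.

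The cost is a wording change and an earlier signature. The small downside is that a few consents will go unused when Scan 1 images prove unusable.
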